## Version History

Version	Date	Notes
1.0	May 15, 2018	SAP approved
1.1	May 21, 2018	Amendment: 

• Updated Nash Resolution Responder Definition by excluding the third criteria of no worsening in fibrosis and adding requirement for at least a 2-point reduction in NAS to NASH Resolution Responder.

• Added endpoints related to NAS, fibrosis and NASH resolution responders.

1.2		Amendment: 

• Reconciled differences in SAP 1.1 in endpoints as defined in sections 2.1, 2.3 and 3.7.3

• Added exploratory analyses for Extension study

## **1. INTRODUCTION**

This document provides a description of the statistical methods and procedures to be implemented for the analyses of data from the study with protocol number MGL-3196-05, Amendment 4, 02 August 2017. Any deviations from this Statistical Analysis Plan (SAP) will be documented in the final clinical study report.

## **2. STUDY OBJECTIVES AND STUDY DESIGN**

### **2.1 Study Objectives**

#### **2.1.1 Primary Objective**

The primary objective of this study is to determine the effect of once-daily oral MGL-3196 80 mg versus placebo (randomized 2:1) for 12 weeks on the percent change in hepatic fat fraction by proton density fat fraction magnetic resonance imaging (MRI-PDFF) from baseline in patients with biopsy proven NASH.

#### **2.1.2 Secondary Objectives**

The secondary objectives of the study are the following:

- To evaluate the safety and tolerability, including any changes in thyroid axis hormones, of once-daily oral MGL-3196 80 mg versus placebo after 12 and 36 weeks in patients with biopsy-proven NASH;
- To evaluate the effect of once-daily oral MGL-3196 80 mg versus placebo for 36 weeks on the percent change in hepatic fat fraction by MRI-PDFF from baseline in patients with biopsy-proven NASH;
- To evaluate the effect of once-daily oral MGL-3196 80 mg versus placebo for 12 and 36 weeks on the change in hepatic fat fraction by MRI-PDFF from baseline in patients with biopsy-proven NASH; and
- To evaluate the effect of once-daily oral MGL-3196 80 mg versus placebo for 12 and 36 weeks on the number of patients achieving  $\geq 30\%$  relative fat reduction at Weeks 12 and 36 (MRI-PDFF Responders)
- To determine the effect of once-daily oral MGL-3196 80 mg versus placebo after 12 and 36 weeks in patients with biopsy-proven NASH on:
  - High-sensitivity C-reactive protein (hsCRP);
  - Serum alanine aminotransferase (ALT) and aspartate aminotransferase (AST);
  - Lipid parameters including low-density lipoprotein cholesterol (LDL-C), high-density lipoprotein cholesterol (HDL-C), non-HDL-C, total cholesterol (TC), triglycerides (TG), apolipoprotein B (ApoB), and lipoprotein(a) (Lp[a]) particles, ApoCIII; and
  - NASH and fibrosis biomarkers including cytokeratin-18 (CK-18), fibrosis-4 (FIB-4), ProC3, and enhanced liver function (ELF) test.
  -

### 2.1.3 Liver Biopsy Secondary and Exploratory Objectives

Responder variables at Week 36 include:

- NASH Biopsy Responders:
  - The number and percentage of patients achieving a 1-point reduction in NAS;
  - the number and percentage of patients achieving a 2-point reduction in NAS at 36 weeks;
  - the number and percentage of patients achieving a 2-point reduction in NAS at 36 weeks; and either  $\geq 1$  point reduction in lobular inflammation or  $\geq 1$  point reduction in hepatocellular ballooning; and
  - the number and percentage of patients achieving a 2-point reduction in NAS at 36 weeks; and no worsening of fibrosis.
- NASH Component Responder definition (only requires one or more criteria):
  - reduction in hepatocellular steatosis; or
  - reduction in lobular inflammation; or
  - reduction in hepatocellular ballooning.
- Fibrosis Responders:
  - the number and percentage of patients achieving  $\geq 1$  stage reduction in fibrosis;
  - the number and percentage of patients achieving  $\geq 1$  stage reduction in fibrosis; and no worsening of NAS; and
  - the number and percentage of patients achieving  $\geq 2$  stage reduction in fibrosis.
- NASH Resolution Responder Definition (requires both criteria):
  - lobular inflammation = 0 or 1; and
  - hepatocellular ballooning = 0.
- NASH Resolution Responders with at least a 2-point reduction in NAS at Week 36.
- [REDACTED]
- [REDACTED]
- The number and percentage of patients achieving a change in NASH diagnosis (ie, from definite NASH to not-NASH based on histology) from baseline to Week 36.

Other liver biopsy analyses include:

- [REDACTED]
- The change in portal inflammation from baseline at 36 weeks; and

- Correlation of reduction of liver fat on MRI-PDFF at 12 and 36 weeks with improvement or resolution of NASH on liver biopsy.
- Liver biopsy analyses performed on prespecified and data driven groups.

#### 2.1.4 Tertiary/Exploratory Objective

Term	Percentage
GMOs	75%
Organic	65%
Natural	60%
Artificial	55%

### 2.1.5 Extension Study Exploratory Objectives

## **2.2 Study Design**

The population for this study is male and female patients  $\geq 18$  years of age with biopsy-proven NASH.

This is a multi-center, double-blind, randomized, placebo-controlled study to evaluate the safety and efficacy of MGL-3196 in patients with NASH. Patients who qualify for study inclusion will be randomized to receive one of two 36-week treatments: MGL-3196 80 mg or placebo given orally once-daily in the morning. Following 12 weeks of treatment, the primary endpoint, percent change from baseline in hepatic fat fraction measured by MRI-PDFF, will be evaluated. At 36 weeks, all patients will undergo liver biopsy.

Following randomization, patients will begin the initial 12-week Treatment Period. Patients will undergo liver MRI-PDFF prior to the start of treatment (pre-dose), at the end of the initial 12-week Treatment Period (12 weeks after the start of treatment), and after continuing blinded treatment (MGL-3196 or placebo) for an additional 24 weeks (36 weeks after the start of treatment). A liver biopsy will be obtained prior to start of treatment (pre-dose) if the patient has not had a qualifying liver biopsy within 180 days of randomization and at 36 weeks. During the study, patients will return to the study site periodically for assessment of vital signs (temperature, pulse, respiratory rate, and seated blood pressure), 12-lead electrocardiogram (ECG), and clinical laboratory testing (hematology, chemistry, and urinalysis). Blood samples will be collected at specified times for the assessment of lipid parameters, thyroid hormone

parameters, and other biomarkers. Patients will be evaluated for adverse events (AE) and concomitant medication use throughout the study. Patients should be monitored throughout the study for clinical signs and symptoms of hyper- or hypothyroidism.

A PK assessment will be made at Week 2 including a pre-dose fasting determination and assessments at 2, 4, 6, and 8 hours postdose. As described in the PK section, patients who have a calculated  $AUC_{inf} \leq 5500$  ng\*hr/ml (combined MGL-3196 and MGL-3196-M1) will continue on 80 mg. As described in Section 8, patients (~10%) with an  $AUC_{inf} \leq 3000$  ng\*hr/ml who are predicted to have exposure at 100 mg that remains  $AUC \leq 5550$  based on a conservative calculation, the MGL-3196 dose will be increased from 80 mg to 100 mg at the Week 4 visit. For patients with combined  $AUC > 5500$  ng\*hr/ml, the dose of MGL-3196 will be reduced to 60 mg per day at the Week 4 visit. Patients with  $AUC_{inf} > 11,000$  (combined MGL-3196 and M1) plus an SHBG>150% increase from baseline at Week 2 (indicative that average or steady-state exposure is  $> 11,000$  ng\*hr/ml) will be downtitrated to 40 mg at Week 4. If SHBG  $\leq 150\%$ , then the patient will be downtitrated to 60 mg at Week 4, and the patient's 4 Week SHBG and predose concentrations will be evaluated. If at Week 4 SHBG  $> 150\%$  increase from baseline and predose  $> 40$ ng/ml for MGL-3196 and  $> 40$ ng/ml for M1, then the patient will be down-titrated to 40 mg at the Week 8 visit.

A combined MGL-3196 and MGL-3196-M1 exposure  $\leq 5500$  ng\*hr/ml has not demonstrated a drug-related decrease in FT4 to  $< LLN < 0.7$  ng/dL) in Phase 1 studies. However, patients with NASH without symptoms of hypothyroidism may occasionally have low baseline levels of FT4, with normal FT3 and TSH, and are not clinically or subclinically hypothyroid. Low FT4 in the presence of normal FT3 (active hormone) and TSH is not consistent with hypothyroidism; low FT4 is observed in euthyroid (formerly hypothyroid) patients treated with T3 monotherapy 

In patients continuing on 80 mg MGL-3196 ( $AUC_{inf} < 5500$ ) who have FT4 LLN ( $>.55$  to  $<.7$  ng/dL):

At Week 4 or later:

- If FT3 remains normal (not decreased to  $<LLN$ ) and TSH remains normal, and the patient does not have symptoms of hypothyroidism, the patient may continue on the current dose.
- Down-titration to 60 mg may be made at the next visit, Week 8 or later if FT4  $<LLN$  ( $>.55$  to  $<.7$  ng/dL), FT3 and TSH are normal, and there is evidence that the decrease in FT4  $<LLN$  ( $>.55$  to  $<.7$  ng/dL) is drug-related including a  $>30\%$  decrease from baseline in FT4, an increase in SHBG  $>120\%$  from baseline and predose exposure  $>40$  ng/ml for MGL-3196 and  $> 40$  ng/ml for MGL-3196-M1 that is consistent with increased drug exposure relative to the Week 2 PK assessment.

In patients down-titrated to 60 mg at Week 4 who have FT4 LLN ( $>.55$  to  $<.7$  ng/dL):

- At Week 8 or later, if FT3 and TSH remain normal, the patient does not have symptoms of hypothyroidism, the patient may continue on the current dose.
- Down-titration to 60 or 40 mg may be made at the next visit, Week 12 or later if FT4  $<LLN$  ( $>.55$  to  $<.7$  ng/dL), FT3 and TSH are normal, and there is evidence that the decrease in FT4  $<LLN$  ( $>.55$  to  $<.7$  ng/dL) is drug-related including a  $>30\%$  decrease

from baseline in FT4, an increase in SHBG >120% from baseline and predose exposure >40 ng/ml for MGL-3196 and > 40 ng/ml for MGL-3196-M1 that is consistent with increased drug exposure relative to the Week 2 PK assessment.

If these conditions are not met, the patient will continue on current dose and thyroid indices reassessed at subsequent visits. Any randomized patients previously down-titrated based on LLN FT4 per Protocol Amendment 2 who did not meet these criteria for down-titration (Amendment 3) will be returned to the previous dose in a blinded fashion at the next visit.

If FT4 is  $\leq .55$  ng/dL on 80 or 60 mg dose with normal FT3 and TSH (which are unblinded to study personnel for all patients), even if the decrease in FT4 is not felt to be primarily drug-related, a down titration to 60 or 40 mg, respectively, may be made at the next visit as determined by Sponsor and Medical Monitor after blinded review. If it is determined after blinded review by Sponsor and Medical Monitor that thyroid therapy should be initiated, because thyroxine cannot be initiated without breaking the blind, the patient will be discontinued from the study and Early Termination assessments will be performed.

A Data Safety Monitoring Board (DSMB) will oversee the study to ensure patient safety and to advise if any dosing alterations are recommended. The DSMB will review safety, including thyroid hormone effects, liver-related events (ie, clinically meaningful elevations in liver enzymes ALT, AST, and bilirubin), cardiovascular assessment (ie, changes in ECG, cardiac biomarkers, cardiac AEs, cardiac symptoms, arrhythmias, etc.), SAEs for trends in causality, and other efficacy (lipid parameters) and safety data as needed. The DSMB will perform regularly scheduled reviews the first will be scheduled when 25 patients have received 6 weeks of treatment. Additional regularly timed meetings will be held and ad hoc meetings may also occur at the discretion of by Madrigal and the DSMB.

The schedule of procedures can be found in Protocol Appendix A.

### **2.2.1 Extension Study**

An open label active treatment 36 Week extension study was conducted in patients completing the Main Study for patients who consented to the Extension study and met the inclusion criterion of significant elevation in liver enzymes at Week 30 of the main study as defined in Protocol Amendment 6. The treatment code was unknown for patients entering the extension study, but treatment code was revealed while the Extension study was ongoing. Patients randomized to MGL-3196 during the Main study remained on the same dose of MGL-3196 or had a prespecified increase in dose upon entering the Extension study. Former placebo patients were treated with 80 mg MGL-3196 initially, then uptitrated to 100 mg, remained on 80 mg or had their dose reduced to 60 mg at Week 4 based on a PK sample at Week 2. During the Extension study, based on additional safety results from the Main study, all Extension study patients had doses adjusted to at least 80 mg per day, and several Extension study patients took 100 or 120 mg per day.

## 2.3 Study Endpoints

### 2.3.1 Efficacy Variables

#### 2.3.1.1 MRI-PDFF Assessments

The primary efficacy variable is percent change in hepatic fat fraction by MRI-PDFF from baseline at 12 weeks for MGL-3196 80 mg versus placebo in patients with biopsy-proven NASH.

The other related efficacy variables with MRI-PDFF at Week 12 are:

- Change in hepatic fat fraction by MRI-PDFF from baseline;
- Proportion of patients who have 30% or more reduction in hepatic fat fraction by MRI-PDFF from baseline at Week 12, that is, the percent change from baseline to Week 12 is  $\leq -30\%$ ;
- Proportion of patients who have 5% or more absolute reduction in hepatic fat fraction by MRI-PDFF from baseline at Week 12, that is, the change from baseline to Week 12 is  $\leq -5\%$  in hepatic fat; and
- Proportion of patients who have 5% or less hepatic fat fraction by MRI-PDFF at Week 12, that is, the hepatic fat fraction measurement at Week 12 is  $\leq 5\%$ .

The efficacy variables at Week 36 include:

- Five efficacy endpoints in hepatic fat fraction by MRI-PDFF as specified in the primary Week 12 efficacy endpoint from baseline at 36 weeks for MGL-3196 80 mg versus placebo;

#### 2.3.1.2 Liver Biopsy Assessments

- NASH Biopsy Responders:
  - The number and percentage of patients achieving a 1-point reduction in NAS;
  - the number and percentage of patients achieving a 2-point reduction in NAS at 36 weeks;
  - the number and percentage of patients achieving a 2-point reduction in NAS at 36 weeks; and either  $\geq 1$  point reduction in lobular inflammation or  $\geq 1$  point reduction in hepatocellular ballooning; and
  - the number and percentage of patients achieving a 2-point reduction in NAS at 36 weeks; and no worsening of fibrosis.
- NASH Component Responder definition (only requires one or more criteria):
  - reduction in hepatocellular steatosis; or
  - reduction in lobular inflammation; or
  - reduction in hepatocellular ballooning.

- Fibrosis Responders:
  - the number and percentage of patients achieving  $\geq 1$  stage reduction in fibrosis;
  - the number and percentage of patients achieving  $\geq 1$  stage reduction in fibrosis; and no worsening of NAS; and
  - the number and percentage of patients achieving  $\geq 2$  stage reduction in fibrosis.
- NASH Resolution Responder Definition (requires both criteria):
  - lobular inflammation = 0 or 1; and
  - hepatocellular ballooning = 0.
- NASH Resolution Responders with at least a 2-point reduction in NAS at Week 36.
- Other exploratory NASH Resolution Responders:
  - [REDACTED]
  - [REDACTED]
- The number and percentage of patients achieving a change in NASH diagnosis (ie, from definite NASH to not-NASH based on histology) from baseline to Week 36.

Other liver biopsy analyses include:

- [REDACTED]
- The change in portal inflammation from baseline at 36 weeks; and
- [REDACTED]
- Correlation of reduction of liver fat on MRI-PDFF at 12 and 36 weeks with improvement or resolution of NASH on liver biopsy.

#### 2.3.1.3 Other safety and efficacy variables include the following:

- The change in thyroid axis hormones from baseline at 12 and 36 weeks for MGL-3196 80 mg versus placebo;
- The percent change from baseline to Week 12 and 36 in SHBG;
- The change in hsCRP, ALT, AST, GGT, direct LDL-C, HDL-C, non-HDL-C, TC, TG, ApoB, Lp(a), ApoCIII, CK-18, FIB-4, Pro-C3, and ELF test from baseline at 12 and 36 weeks for MGL-3196 80 mg versus placebo, including pre-specified baseline cutoffs for ALT, LDL-C, Lp(a) and fibrosis biomarkers;
- The change in HR-QoL SF-36 scores from baseline at 12 and 36 weeks for MGL-3196 80 mg versus placebo;

- The change in glucose, insulin, HOMA-IR, HbA1c, NEFA, adipo-IR, and adiponectin from baseline at 12 and 36 weeks for MGL-3196 80 mg versus placebo;
- The change in body weight, BMI, waist circumference, waist-hip ratio, and blood pressure from baseline at 12 and 36 weeks for MGL-3196 80 mg versus placebo;
- The correlation between plasma MGL-3196 exposure to changes in efficacy and safety biomarkers;
- The correlation between genomic markers of NASH and responses to MGL-3196;
- The correlation in reduction of liver fat on MRI-PDFF at 12 and 36 weeks with improvement or resolution of NASH on liver biopsy; and
- The correlation between percent change in SHBG from baseline to Week 12 and 36 with efficacy and safety measurements at Week 12 and 36 visit.

### 2.3.2 Pharmacokinetics

Blood samples for PK assessments will be obtained pre-dose from patients at the Baseline Visit (Day 1), Weeks 2, 4, 8, 16, 24, and 36, and the Early Termination Visit. Patients will be instructed not to take study drug prior to PK sampling at these respective study weeks.

At Week 2 visit, PK assessments will be made in the clinic after over-night fast at pre-dose. An 80 mg dose of MGL-3196 or placebo will be administered and PK assessments will be made at 2, 4, 6, and 8 hours post dose. Total  $AUC_{inf}$  will be calculated for MGL-3196 and MGL-3196-M1 based on Week 2  $AUC_{(0-8)}$ , exposure at 8 h and historic geometric mean elimination rate constant for MGL-3196 and MGL-3196-M1 at the 80 mg dose. Modeling based on historic data obtained for the 80 and 100 mg doses indicate that, using this approach,  $AUC_{actual}$  ( $AUC_{(0-24)}$ ) is estimated within 1.8%, SD 5.4% for MGL-3196 given at a dose of 80 mg and is slightly over estimated for MGL-3196-M1 AUC by 5.7% SD 8.5% at a dose of 80 mg. Similar results were obtained for a 100 mg dose. Dose adjustment will be made to 60 mg once per day for any patients whose combined estimated MGL-3196 and MGL-3196-M1 ( $AUC_{(0-24)}$ ) at 2 weeks on the 80 mg dose exceeds 5500 ng\*hr/ml. All subjects previously dosed at 50 mg MGL-3196 had combined MGL-3196 plus MGL-3196-M1 less than 5500 ng\*hr/ml, geo mean= 3400 ng\*hr/ml. Notably, the trough pre-dose drug levels obtained at 50 -100 mg in the MAD study are also predictive of subjects' relative AUCs at a given dose. For patients whose combined estimated  $AUC_{(0-24)}$  at 2 weeks at the 80 mg dose is  $>11,000$  ng\*hr/ml, plus SHBG $>150\%$  increased from baseline, the dose will be decreased to 40 mg at the 4 Week visit (or later per Synopsis), because, even given the greater than dose proportionate increase in exposure between a 60 and 80 mg dose, the exposure at 60 mg may be  $\geq 5500$  ng\*hr/ml. For patients whose combined estimated  $AUC_{(0-24)}$  at 2 weeks at the 80 mg dose is  $\leq 3000$  ng\*hr/ml, the dose will be increased to 100 mg at the 4 Week visit. As based on conservative estimates, the predicted exposure at 100 mg will be significantly  $\leq 5500$  ng\*hr/ml. This prediction is based on data obtained in healthy volunteers in which there is greater than dose proportionate increases in MGL-3196 between 80 and 100 mg daily doses, and less than dose proportionate increases in MGL-3196-M1 between 80 and 100 mg doses. Pharmacokinetic data (blinded to patient ID) obtained from the first 21 patients randomized to MGL-3196 suggests that there are no clear differences in MGL-3196 or MGL-3196-M1 exposure at the 80-mg dose between healthy volunteers and NASH patients enrolled in this study.

### **2.3.3 Safety Endpoints**

Safety variables to be assessed include safety laboratory tests, vital signs and anthropometrics, 12-lead ECG with rhythm strip, dual-energy x-ray absorptiometry, physical examinations, adverse events, and clinical assessments.

## **3. STATISTICAL METHODOLOGY**

### **3.1 Baseline, Endpoint, and Other Statistical Considerations**

Baseline for all efficacy and safety variables will be defined as Baseline visit (Day 1). If the measurement at this visit is missing, the last measurement prior to the first dose of randomized study drug will be used.

For efficacy variables other than hepatic fat fraction, early termination and unscheduled visits will be assigned a visit number based on the date of assessment relative to the first dose of the double-blind study drug. Visit windows will be defined as the scheduled time from dosing date with a 7-day window ( $\pm 7$  days). Within a visit window, if a scheduled visit occurs, then the measurement from this scheduled visit will be used as the measurement for this visit window. If no scheduled visit occurs within a visit window, the last measurement within the window will be used. If no visits occur within a visit window, the measurement of this visit will be treated as missing.

If the last dose date is missing due to subject lost to follow-up, then it will be assumed the subject is still on study drug at the last clinic visit. For lipids measurements, only data up to one day after the last dose will be considered valid and used in the analyses. For MRI-PDFF and liver biopsy results, the measurements up to three weeks after the last dose will still be considered valid and used in the analyses. For liver enzyme measurements, all the measurements will be used whether the subject is on or off study drug at the clinic visit.

If weight is missing at the Week 12 (or Week 36) visit and the subject completed the Week 12 (or Week 36) visit, the average of the weight at the previous scheduled visit and next scheduled visit will be used as the Week 12 (or Week 36) measurement.

Descriptive statistics (number of patients, mean, standard deviation, median, minimum, and maximum) will be used to summarize the continuous data. Discrete measures will be summarized using counts and percentages.

### **3.2 Analysis Populations**

#### **3.2.1 Intent-to-Treat Population**

The Intent-to-Treat (ITT) Population will include all patients who are randomized in the study and receive at least 1 dose of study drug.

#### **3.2.2 Modified Intent-to Treat Population**

The modified intent-to-treat (mITT) population includes all patients who were randomized in the study, received at least 1 dose of study drug, and had lipid and other efficacy measurements at Week 4 or later visits. The mITT population will be used for all secondary efficacy analyses.

### **3.2.3 MRI-PDFF Evaluable Population**

The MRI-PDFF Evaluable population includes all patients who were randomized in the study, received study drug, finished Week 12 Visit, with valid MRI-PDFF measurements at both baseline and Week 12 Visit.

### **3.2.4 Liver Biopsy Evaluable Population**

The liver biopsy evaluable population includes all patients who were randomized in the study, received study drug, with two valid evaluable liver biopsies, one at baseline and one post-treatment. In addition to the following per-protocol populations, additional analyses on the liver biopsy evaluable population will be performed using a Posthoc Per-Protocol Population, as warranted.

### **3.2.5 12-Week Per Protocol Population**

The 12-Week Per Protocol Population will include all MRI-PDFF Evaluable patients who do not have any major protocol deviations during the first 12 weeks. The following criteria will be evaluated for major deviations prior to unblinding of the treatment allocation:

- No eligibility criterion violations;
- Did not discontinue study drug prior to Week 12;
- Patients who are <=75% compliant over the course of the initial 12-week Treatment Period and/or the period between Week 8 and Week 12;
- Not taken any prohibited concomitant medication during 12-week Treatment Period;
- Not unblinded during the 12-week double-blind treatment period; and
- No other substantial protocol violations during 12-week Treatment Period.

The 12-Week Per Protocol Population will be used to assess robustness of the analysis of hepatic fat fraction results of MRI-PDFF during the 12-week Treatment Period.

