5.5.4 Treatment Compliance

Patients will be assessed for study drug compliance at each visit. At Day 1, patients will receive a study drug journal in which to record study drug compliance. Site staff will record the number of capsules taken from each study drug bottle and record this information in the patient's eCRF. If at any visit the patient is <80% compliant, the patient will be counseled on the importance of compliance to the study regimen. If at the end of study, the patient is <80% compliant over the course of the initial 12-week Treatment Period, the patient will not be included in the Per Protocol Population.

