10 STATISTICS

10.1 Analysis Populations

The Intent-to-Treat (ITT) Population will include all patients who are randomized in the study and receive at least 1 dose of study drug. The ITT Population will be used for all efficacy analyses.

The Per Protocol Population will include all ITT patients who finish the Week 12 visit with valid MRI-PDFF measurements and do not have any major protocol deviations. Patients who are <80% compliant over the course of the initial 12-week Treatment Period will not be included in the Per Protocol Population.

The Safety Population will include all patients who are randomized in the study and receive at least 1 dose of study drug and will be used for all safety analyses.

Demographics, disposition, and study populations will be summarized descriptively.

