### **3.2.6 36-Week Per Protocol Population**

The 36-Week Per Protocol Population will include all MRI-PDFF Evaluable patients who have a Week 36 MRI-PDFF measurement, and a baseline and Week 36 liver biopsy.

The 36-Week Per Protocol Population will be used to assess robustness of the analysis of hepatic fat fraction results of MRI-PDFF during the 36-Week period.

Additional potential patients may be excluded from Week 36 Per Protocol Population if the patients:

- Take any prohibited concomitant medication during 12-36 week Treatment Period; or
- Patients who are <=75% compliant over the course of the 12-36 week Treatment Period and/or the period between Week 30 – 36.

Please note that non-compliance from Week 30-36 is not per protocol for Week 36 laboratory tests and Week 36 MRI-PDFF; non-compliance between Week 30-36 with drug compliance for Weeks 12-36 >75% are per protocol for liver biopsy.

For patients who are in the Week 36 Per Protocol Population with Week 36 liver biopsy measured more than two weeks of last dose date, these liver biopsy values will not be used in the Week 36 Per Protocol analysis for liver biopsy responders.

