### **3.6 Study Medication Exposure and Compliance**

Days of exposure to study medication will be summarized by treatment group for the Safety Population using descriptive statistics. Exposure in days is defined as the date of last dose of study drug minus the date of first dose of study drug plus 1. In addition, a contingency table will be provided to display the number and percentage of patients with exposure in the following categories:

- 1 to  $\leq$ 2 weeks (1-14 days),
- $>2$  to  $\leq$ 4 weeks (15-28 days),
- $>4$  to  $\leq$ 8 weeks (29-56 days);
- $>8$  to  $\leq$ 12 weeks (57-84 days),
- $>12$  to  $\leq$ 36 weeks (84-252 days), and
- $>36$  weeks (253 days or more).

Compliance will be calculated based on the total actual number of capsules taken as compared to the total expected number of capsules taken (2 per day). Percent compliance with the study medication during the 12-week Treatment Period (from Week 4 through Week 12) and the whole 36-week Treatment Period (from Week 4 through Week 36) will be summarized by treatment group for the Safety Population using descriptive statistics. Additionally, the number and percentage of patients within each treatment group with overall compliance in the following categories: <80%, 80% to 120%, and >120%, will be provided.

All the patients randomized to the active study drug group will take MGL-3196 80 mg. Based on the PK assessment and SHBG at Week 2, the dose at Week 4 may stay at 80 mg, it may be increased to 100 mg, or it may even be reduced to 60 mg. At Week 8 visit, the dose may be reduced to 40 mg. Duration of each dose level will be summarized, and number/percentage of patients taking each dose at each visit will be tabulated.

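### Per-protocol sets: the compliance cut differs between protocol and SAP, and the 36-Week set as written does not apply the major-deviation criteria for the first 12 weeks

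*SAP*

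**What the plan says.** **Protocol.** There is one Per Protocol Population: ITT patients who finish Week 12 with valid MRI-PDFF measurements and no major deviation. Section 10.1 adds: "Patients who are <80% compliant over the course of the initial 12-week Treatment Period will not be included in the Per Protocol Population". The Synopsis repeats this rule, and section 5.5.4 applies the same cut where "the patient is <80% compliant over the course of the initial 12-week Treatment Period".

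**SAP 3.2.5 (12-Week set).** The base is the MRI-PDFF Evaluable population without major deviations in the first 12 weeks. The list opens with "The following criteria will be evaluated for major deviations prior to unblinding of the treatment allocation". Five of its six bullets state what a per-protocol patient satisfies, for example "Did not discontinue study drug prior to Week 12". The sixth, on compliance, reads "Patients who are <=75% compliant over the course of the initial 12-week Treatment Period and/or the period between Week 8 and Week 12".

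**SAP 3.2.6 (36-Week set).** The base is again MRI-PDFF Evaluable, now also requiring a Week 36 scan and both biopsies. Further exclusions are introduced by "Additional potential patients may be excluded from Week 36 Per Protocol Population if the patients". The two that follow are prohibited medication in Weeks 12-36, and compliance of 75% or less over Weeks 12-36 and/or Weeks 30-36.

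**SAP 3.6.** The compliance summaries are for "Percent compliance with the study medication during the 12-week Treatment Period (from Week 4 through Week 12"), with two capsules expected per day.

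**Use of the sets.** SAP 3.7.2 repeats the hepatic fat analyses on the 12-Week set. SAP 3.7.2.5 repeats the Week 36 MRI-PDFF analysis on the 36-Week set. SAP 3.2.6 also sets a rule for which biopsies count in the per-protocol responder analysis.

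**The concern.** A per-protocol analysis is informative only if membership follows from a fixed rule. Here an analyst working from the protocol and one working from the SAP would classify some patients differently. The 36-Week set has a separate problem: a patient removed from the 12-Week set for an eligibility violation can count as per protocol 24 weeks later, because the list for the later set does not look back before Week 12. Its listed exclusions are also permissive, and SAP 3.2.6, unlike 3.2.5, does not say they are settled before unblinding.

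If the main and per-protocol results agree, these definitions matter little. If they differ, the reader needs to know that the difference does not come from an unsettled or discretionary choice of patients.

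**Working it through.** The plan gives no figure to reproduce on this point. The check compares the texts and applies capsule arithmetic to hypothetical patients.

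**Inputs.** Two capsules per day (SAP 3.6); cuts of <80% (protocol 10.1) and <=75% (SAP 3.2.5); windows of Weeks 0-12 and Weeks 8-12. I read *and/or* in SAP 3.2.5 as meaning that either window is enough.

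**Expected capsules.**
- Weeks 0-12: 84 × 2 = 168
- Weeks 0-4: 28 × 2 = 56
- Weeks 4-12: 56 × 2 = 112
- Weeks 8-12: 28 × 2 = 56

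**Rules in capsules.**
- Protocol excludes if taken/168 < 0.80. Since 0.80 × 168 = 134.4, this means 134 or fewer.
- SAP excludes if taken/168 <= 0.75 (126 or fewer), or if taken in Weeks 8-12 / 56 <= 0.75 (42 or fewer).

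**12-week status.**

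| Patient | Weeks 0-12 | Weeks 8-12 | Protocol | SAP 3.2.5 |
|---|---|---|---|---|
| A | 127-134 of 168 = 75.6%-79.8% | at least 43 of 56 = 76.8% | out | in |
| B | 131 of 168 = 78.0% | 42 of 56 = 75.0% | out | out |
| C | 168 - 14 = 154 of 168 = 91.7% | 56 - 14 = 42 of 56 = 75.0% | in | out |

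The SAP rule is looser than the protocol for A and stricter for C. B shows that a patient between 75% and 80% need not change status.

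**36-week status.** Patient D takes half the capsules in Weeks 0-12 (84/168 = 50.0%) and all of them in Weeks 12-36. D fails both 12-week cuts. For the 36-Week set:
- SAP 3.2.3 (MRI-PDFF Evaluable) requires randomization, dosing, the Week 12 visit and valid scans. It has no deviation or compliance condition.
- SAP 3.2.6 looks only at prohibited medication and compliance from Week 12 onward.

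Given the required scans and biopsies, no listed rule removes D. The same holds for a patient with an eligibility violation, an unblinding, or prohibited medication confined to the first 12 weeks.

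**Start of counting (minor).** Patient E takes nothing in Weeks 0-4 and everything afterwards. From Day 1, compliance is 112/168 = 66.7%. If dosing is counted only from Week 4, it is 112/112 = 100%. With perfect intake after Week 4, missing 34 of the first 56 capsules breaches the protocol cut (134/168 = 79.8%), and missing 42 meets the SAP cut (126/168 = 75.0%). Neither would show if counting began at Week 4.

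**The case against.** - **Direction of the compliance bullet.** A reader might infer that SAP 3.2.5 selects the non-compliant patients. It does not support that. The list is introduced as deviations to be evaluated, and SAP 3.2.6 uses the same <=75% wording as an exclusion. The intent is clear, and this is a drafting slip.
- **Week 4 start.** A reader might infer that the first month of dosing is definitely left out. The phrase sits in SAP 3.6, which describes summaries for the Safety Population, not in 3.2.5. Drug is dispensed at baseline and next at Week 4, so the phrase may refer to capsule-count visits that cover dosing from Day 1. SAP 3.6 also describes Week 4 through Week 36 as the whole 36-week period, which fits that reading. Against it, accountability is already assessed at Week 2. The text is ambiguous, and patient E shows the effect of one reading only.
- **Unblinding.** A reader might infer that the 36-Week set can be freely redrawn once codes are known. SAP section 5 requires the derived database specification to be final before database lock and unblinding, which answers part of this. It does not turn a permissive exclusion into a rule. The documents also do not show that per-protocol membership was changed after code release: the SAP version history lists no change to these sets.
- **Separate 36-Week base.** Using later windows for a later endpoint is defensible. Full nesting would permanently drop a patient for one poor Week 8-12 interval despite good later compliance. The word *additional* in 3.2.6 may also have been meant to build on the 12-week exclusions. Both points bear on the remedy, but the stated base population is still MRI-PDFF Evaluable.
- **Importance.** These sets only repeat the main analyses, and the SAP labels the biopsy analyses exploratory. This stands and limits the weight of the point.

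**Conclusion.** The concern holds on two counts. First, the compliance cut changes from <80% in the protocol to <=75% in the SAP, with an added Week 8-12 window and no declaration of the change, so some patients' status differs in one direction or the other. Second, the 36-Week set as written ignores major deviations before Week 12, and its own exclusions are optional with no timing stated in 3.2.6. The bullet direction and the Week 4 phrase are minor wording faults.

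It would be wrong to say that every patient between 75% and 80% changes status; the Week 8-12 window prevents that. It would also be wrong to say that the main MRI-PDFF result is at risk, because in the SAP the main analyses use other populations.

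The number of affected patients cannot be derived, because the documents give no compliance or deviation counts. The capsule examples assume two capsules expected per day over exactly 84 days, and that meeting either SAP window is enough for exclusion. This is worth correcting because the change is cheap.

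**What to change.** Revise SAP 3.2.5, 3.2.6 and 3.6 as follows:

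1. Use the protocol's 80% cut, or declare the 75% cut as a change from the protocol with a reason. Say whether the Week 8-12 window stays.
2. Word every bullet in 3.2.5 in the same direction.
3. State that compliance counts dosing from Day 1.
4. Apply the pre-Week-12 major-deviation criteria (eligibility, unblinding, prohibited medication, overall 12-week compliance) to the 36-Week set. The Week 8-12 window need not carry over.
5. Make the 36-week exclusions mandatory (*will*, not *may*), with membership fixed before unblinding. Label any membership decided later as post hoc.

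The cost is SAP wording and a small change in the size of the sets. The direction of that change for the 12-Week set is not known in advance: returning to 80% removes patients like A, while dropping the Week 8-12 window brings back patients like C. Applying the early criteria can only reduce the 36-Week set.
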